The recommended dose determined by phase I dose escalation is dose level 2-A (DL2-A in section 7.11)

Agent	Dose	Route	Day
nal-IRI	50 mg/m ² (Recommended Dose Determined by Phase I Dose Escalation)	Intravenous over 90 minutes	Days 1 and 15
5-FU	2400 mg/m ²	Intravenous over 46 hours	Day 1 and 15
Rucaparib	600 mg (Recommended Dose Determined by Phase I Dose Escalation)	Oral	Twice daily on Days 4-13 and days 18-27 (Recommended schedule determined by phase I dose escalation)

7.13 Phase II (Phase II study at recommended dose level determined by the Phase I portion)

Agent	Dose	Route	Day
nal-IRI	Recommended Dose Determined by Phase I Dose Escalation	Intravenous over 90 minutes	Days 1 and 15
5-FU	2400 mg/m ²	Intravenous over 46 hours	Days 1 and 15
Rucaparib	Recommended Dose Determined by Phase I Dose Escalation	Oral	Twice daily on days as determined by Phase I administration schedule

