7.42 Definitions of DLT

Toxicity will be assessed using the NCI CTCAE, version 4.03 unless otherwise specified. A DLT is defined as an AE or abnormal laboratory value (assessed as possibly, probably or definitely related to the study medication) which occurs \leq 28 days following the first dose of MFR (or 1 cycles of therapy, each cycle = 28 days), and meets any of the criteria listed in Table 7.421.

If a patient experiences toxicity that fulfills the criteria for a DLT during the DLT observation window (cycle 1 day 1 through cycle 1 day 28, treatment with the study drug will be interrupted and the toxicity will be followed up. Patients will be allowed to remain on study if the DLT is resolved within 4 weeks at the discretion of the investigator. Patients will continue on study at the next lowest dose level. If treatment is reduced during the DLT observation window or is held for >28 days for any reason, this will be considered a DLT.

7.421 Dose Limiting Toxicities (DLT)

TOXICITY	DLT CRITERIA
Hematology	CTCAE grade 4 neutropenia with fever of any duration, or grade 4 neutropenia lasting more than 5 consecutive days
	CTCAE grade 4 thrombocytopenia lasting more than 5 days, or grade 3 with bleeding
	CTCAE Grade 3 or 4 neutropenia with fever (temperature $\geq 38.5^{\circ}\text{C}$)
Skin and subcutaneous tissue disorders	Rash, hand-foot skin reaction or photosensitivity CTCAE Grade 3 lasting more than 7 consecutive days despite skin toxicity treatment (as per local practice)
Gastro-intestinal	CTCAE grade ≥ 3 nausea or vomiting lasting more than or equal to 48 hrs despite optimal anti-emetic therapy
	CTCAE grade ≥ 3 diarrhea lasting more than or equal to 48 hrs despite optimal anti-diarrhea treatment
Hepatobiliary	CTCAE grade ≥ 3 total bilirubin (excluding any elevations caused by mechanical obstruction of the biliary tree by tumor or stent blockage)
	CTCAE grade ≥ 4 ALT (isolated increases in AST without concomitant increases in ALT will not be considered dose-limiting, because of the non-specific nature of AST)
	Serum alkaline phosphatase CTCAE Grade 4 lasting more than 7 consecutive days
ECG QTc Interval	QTc interval ≥ 501 ms on at least two separate consecutive ECGs taken 5 min apart
Renal	Serum creatinine $> 6x$ ULN
Non-hematologic events	Any non-hematological CTCAE grade ≥ 3 , except for the exclusions noted below
Other	Any related toxicity that delays treatment by > 28 days
Exceptions to DLT criteria	CTCAE grade 3 fatigue lasting fewer than 5 days

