	CTCAE grade 3 edema lasting fewer than 5 days
	Grade 3 laboratory abnormalities that are responsive to oral supplementation or deemed by the investigator to be not clinically significant
CTCAE version 4.03 will be used for all grading. Optimal therapy for vomiting or diarrhea will be based in institutional guidelines, with consideration of the prohibited medications listed in this protocol.	

7.5 Phase II - The phase II study in pancreatic cancer will depend on the successful completion of the phase I trial, determination of the recommended dose level and discussion between PI and co-sponsors of the study.

7.51 Following the accrual of the first 6 patients into the phase II portion, we will assess for any unexpected serious toxicities (without halting accrual). If >1 of the first 6 patients experience grade 5 toxicity at least possibly (possible, probable, definite) related to treatment, we will halt accrual and discuss with the sponsors alternative dose levels including the possibility to de-escalate to one dose level. After reinitiating accrual, the patients who were included in the prior dose level cannot be considered for the final analysis and will have to be replaced.

7.52 In the Phase II portion of this study, all patients' tissue samples will be screened for HRD and BRCA-like signature, and only those patients with defects will be selected for the treatment study.

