8.0 Dosage Modification Based on Adverse Events

Strictly follow the modifications in this table for the first **two** cycles, until individual treatment tolerance can be ascertained. Thereafter, these modifications should be regarded as guidelines to produce mild-to-moderate, but not debilitating, side effects. If multiple adverse events are seen, administer dose based on greatest reduction required for any single adverse event observed. Reductions or increases apply to treatment given in the preceding cycle and are based on adverse events observed since the prior dose.

ALERT: *ADR reporting may be required for some adverse events (See Section 10)*

8.1 Dose Modifications for Rucaparib (Based on Adverse Events in Tables 8.2 and 8.3)

Starting Dose Level	1 st Dose Modification	2 nd Dose Modification
600 mg BID	500 mg BID	400 mg BID
400 mg BID	300 mg BID	200 mg BID
300 mg BID	200 mg BID	300 mg QD
200 mg BID	300 mg QD	200 mg QD

NOTE: No more than two dose reductions are allowed.

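### The Phase I DLT rules can score a slower-recovering toxicity more favourably than a faster one, and the catch-all row of Table 7.421 has no stated precedence

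*Combined protocol and SAP*

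**What the plan says.** Section 7.42 defines a DLT as a treatment-related event within 28 days of the first dose that meets any criterion in Table 7.421. It then adds: "If treatment is reduced during the DLT observation window or is held for >28 days for any reason, this will be considered a DLT".

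Within the table, afebrile neutropenia counts only at grade 4 for more than 5 days. Nausea, vomiting and diarrhea count at grade 3 or higher only from 48 hours, and grade 3 rash only beyond 7 days. The alkaline phosphatase criterion is "Serum alkaline phosphatase CTCAE Grade 4 lasting more than 7 consecutive days". A further row takes every non-hematologic event of grade 3 or higher, "except for the exclusions noted below". Those exclusions are short grade 3 fatigue, short grade 3 edema, and "Grade 3 laboratory abnormalities that are responsive to oral supplementation or deemed by the investigator to be not clinically significant".

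Dose changes in cycle 1 are binding. Section 8.0 reads "Strictly follow the modifications in this table for the first" two cycles. For grade 3 or 4 neutropenia, Section 8.2 requires a delay until grade 2 or lower and then a 25% cut. Its footnote d extends the delay to all agents, and footnote e applies the cut on resumption.

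Sections 13.4 and 16.227 treat a patient who received 75% or less of the cycle-1 dose, and had no DLT, as uninformative; another patient is enrolled at that level. Section 16.2 puts everyone who received one dose into the analysis, and provides for replacing patients removed in cycle 1 where the cause was not toxicity.

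Section 16.228 makes DL2-A the MTD on fewer than 2 DLTs in 6. Section 7.12 reports the outcome: "The recommended dose determined by phase I dose escalation is dose level 2-A".

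**The concern.** DLT incidence is the Phase I primary endpoint (Section 16.11), and the DL2-A rule has little slack. Two features of the rules bear on that count.

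The first is an ordering problem. The reduction clause depends on a reduced dose being given inside the window. The replacement rule depends on doses being missed. A related toxicity that clears quickly enough for a reduced dose is a DLT. The same toxicity, clearing more slowly, can take the patient out of the DLT denominator. That pushes the count down where tolerance was worse. The case is foreseeable: a blood count is scheduled on Day 15 (Section 4.0), and Section 15.27 lists neutropenia among the most common grade 3 or 4 laboratory abnormalities with nal-IRI plus 5-FU and leucovorin.

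The second is an overlap. Read literally, the catch-all row captures short-lived events that a specific row leaves out, and no sentence says which row prevails.

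**Working it through.** **Plan's own figure.** Section 16.21 gives at least 82% for seeing a toxicity of 25% incidence among 6 patients: 1 − 0.75⁶ = 0.822. It reproduces and is not in dispute.

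**Cycle-1 dose if all agents are held from Day 15 through Day 28** (schedule from Section 7.1):
- nal-IRI and 5-FU: 1 of 2 infusions = 50%.
- Rucaparib: Days 4-13 give 10 × 2 = 20 doses and Days 18-27 another 20; received 20/40 = 50%.

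Each agent is at 50%, below the 75% limit, so it does not matter that Section 13.4 is silent on how the agents combine.

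**Related, afebrile grade 3 neutropenia on Day 15, by time of recovery.** The event meets no row of Table 7.421. The >28-day limb, counted from the missed infusion, starts after Day 15 + 28 = Day 43.

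| Treatment resumes | Cycle-1 dose | Section 7.42 clause | Result |
|---|---|---|---|
| By Day 28, e.g. Day 22 at 75% | 1.75/2 = 87.5% of the reduced infusion | Met: reduced in window | DLT |
| Days 29-43 | 50% of each agent | Not met: delay of 14-28 days | Replaced, no DLT |
| After Day 43 | 50% of each agent | Hold limb met, though the hold ends outside the window | DLT on the wording |

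The middle row is the gap. It assumes that a reduction is dated by the reduced dose. Section 8.2 footnote e supports this by applying the cut on resumption, but Section 7.42 does not say so.

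**Catch-all overlap, with the reduction clause always applied:**
- Grade 3 diarrhea under 48 hours, resolved, with the 25% cut of Section 8.3 given on Day 15: a DLT whether or not the catch-all is applied, because of the clause.
- The same event after the Day 15 infusion, with rucaparib not cut and the next infusion on Day 29: not a DLT if the specific row governs; a DLT if the catch-all is literal. An in-window rucaparib cut (Days 18-27; Sections 8.1 and 8.21) would make it a DLT either way. Footnote b of Section 8.21 may spare controlled diarrhea such a cut.
- Grade 4 alkaline phosphatase for 7 days or less, no cut in the window: not a DLT under its own row; a DLT under the literal catch-all, since the laboratory exception stops at grade 3.
- Short grade 3 nausea or vomiting, and grade 3 rash of 7 days or less, follow the same pattern.

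**Effect on the DL2-A rule:**
- Recorded 1/6 = 16.7%: one reclassified patient gives 2/6 = 33.3%, and the rule fails.
- Recorded 0/6: two reclassified patients are needed.
- Recorded 1/6 plus one replaced patient: 1/7 = 14.3% if kept as a non-DLT, 2/7 = 28.6% if counted as a DLT. The latter meets the two-patient wording of Section 16.228 but is below the one-third in Section 16.21.

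**The case against.** The strongest reply is that the definition is a plain OR: any table row, or the reduction clause. Read so, it gives one count, and a rule stricter than its specific rows is a legitimate conservative choice. Much of this stands. A reader might infer that the reduction clause can be left out, giving further readings of the same records. The text does not support that, because the clause is mandatory. Nor does it conflict with the row for "Any related toxicity that delays treatment by" more than 28 days: the clause simply adds holds for other reasons.

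A reader might also infer that isolated grade 4 AST is caught by the catch-all. It is not; the table states that "isolated increases in AST without concomitant increases in ALT will not be considered dose-limiting".

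What remains is narrower. Applying the catch-all literally leaves the 48-hour and 7-day qualifiers with nothing to do, so the specific row is the natural reading, yet the protocol does not say so.

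On replacement, Section 16.2 points against dropping toxicity cases, and Section 16.227 keeps the toxicity data of replaced patients. But Section 16.2 speaks of removal from study, not of a missed dose in a patient who stays on. Sections 13.4 and 16.227 exempt only DLTs, not related toxicity short of a DLT. The sections sit badly together, and the gap is not closed.

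Controls also exist: immediate contact about DLTs (7.418), Study Chair decisions (16.2), study-team and sponsor discussion of the dose (7.414), and later stopping rules (16.521, 16.522).

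**Conclusion.** The point holds and is minor. On the wording, related toxicity with recovery on Days 29 to 43 can be replaced without a DLT, while faster recovery with a reduced dose is a DLT. This error runs one way, toward a lower count. The catch-all overlap has no known direction, since it depends on which reading the adjudication used, and it affects only events without a dose reduction in the window.

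The first conclusion assumes that reductions are dated by the dose given and that Sections 13.4 and 16.227 were applied as written. Confidence attaches to the wording, not to an effect on the dose.

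A reader might infer that DL2-A was wrongly called the MTD. The documents do not support this: they give no DLT counts, no replacements and no adjudication record. DL2-A is already selected, and the choice also rested on discussion with the sponsor. The issue is how firmly the Phase I conclusion can be stated, and what rules would apply if dose-finding reopened (Section 7.51 allows for de-escalation).

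**What to change.** Keep the original adjudication as primary. For DL2-A, and for DL2-B if anyone was treated there, report a sensitivity DLT count labelled post hoc, always applying the reduction clause:

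1. with the specific rows of Table 7.421 governing;
2. with the catch-all row applied literally;
3. with any patient replaced after a dose omission due to related toxicity kept in the denominator and counted as a DLT.

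Qualify the MTD statement if any DL2-A count reaches 2. Scheduled blood counts fall only on Days 1 and 15, so mark a duration as undetermined where no unscheduled result settles it.

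If dose-finding reopens, amend Sections 13.4 and 16.227 to bar replacement when related toxicity caused the missed dose, and state in Table 7.421 that a specific row overrides the catch-all.

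The cost is one small table from data already collected: related adverse events of any grade (Section 10.531), and the dose-modification and DLT forms (Section 18.1). No new patients are needed. The drawbacks are that the DLT rate may look less favourable and that the tally is post hoc.

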8.0 Dosage Modification Based on Adverse Events

Strictly follow the modifications in this table for the first **two** cycles, until individual treatment tolerance can be ascertained. Thereafter, these modifications should be regarded as guidelines to produce mild-to-moderate, but not debilitating, side effects. If multiple adverse events are seen, administer dose based on greatest reduction required for any single adverse event observed. Reductions or increases apply to treatment given in the preceding cycle and are based on adverse events observed since the prior dose.

ALERT: *ADR reporting may be required for some adverse events (See Section 10)*

8.1 Dose Modifications for Rucaparib (Based on Adverse Events in Tables 8.2 and 8.3)

Starting Dose Level	1 st Dose Modification	2 nd Dose Modification
600 mg BID	500 mg BID	400 mg BID
400 mg BID	300 mg BID	200 mg BID
300 mg BID	200 mg BID	300 mg QD
200 mg BID	300 mg QD	200 mg QD

NOTE: No more than two dose reductions are allowed.

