Grade ≥ 4	
 • Hold rucaparib • Monitor liver function tests weekly until resolution to \leq Grade 2 		Resume with a dose reduction and monitor liver function tests weekly for 3 weeks after restarting.

a. NCI-CTCAE = National Cancer Institute - Common Terminology Criteria for Adverse Events, version 4.03

b. Treatment with rucaparib should be held until the toxicity resolves to \leq CTCAE Grade 2. Twice daily dosing may then be resumed at either the same dose or a lower dose, per investigator discretion. If treatment is resumed at the same dose, and the patient experiences the same toxicity, the dose should be reduced following resolution of the event to \leq CTCAE Grade 2. If the patient continues to experience toxicity, additional dose reduction steps are permitted; however, the investigator should contact ACCRU (see Protocol Resource page) before reducing to 300 mg BID. If a patient continues to experience toxicity despite dose reduction steps to 300 mg BID, or if dosing with rucaparib is interrupted for $>$ 14 consecutive days due to toxicity, treatment should be discontinued, unless otherwise agreed between the investigator and ACCRU.

8.3 Dose Modifications for Non-Hematologic Toxicities Other than grade 3 ALT/AST (follow recommendation by Table 8.22), Fatigue and Grade 3 Anorexia^{a, d}

Worst Toxicity by CTCAE Grade*	na1-IRI	5-FU
Grade 1 diarrhea ^b	Continue same dose	Continue same dose
Grade 1 or 2 including diarrhea (except alopecia, nausea and vomiting)	Withhold na1-IRI then resume once resolved to grade 1 at 100% of previous dose	Withhold 5-FU, then resume once resolved to grade 1 at 100% of previous dose, except for Grade 2 hand foot syndrome, Grade 2 cardiac toxicity, or any grade neurocerebellar toxicity
Grade 3 or 4, including diarrhea ^c (except alopecia, nausea and vomiting)	Withhold na1-IRI then resume once resolved to grade 1 per below: 1 st occurrence: Reduce dose to by 25% 2 nd occurrence: Reduce dose another 25% (50% of original dose)	Withhold 5-FU then resume once resolved to grade 1 per below: 1 st occurrence: Reduce dose by 25% 2 nd occurrence: Reduce dose another 25% (50% of original dose) *except for Grade 3 or 4 hand foot syndrome

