Grade 3 or 4 nausea and/or vomiting, despite anti-emetic therapy	Optimize anti-emetic therapy AND reduce dose to 50 mg/m ² , if starting dose is 70 mg/m ² .. If the patient is already receiving 50 mg/m ² , reduce dose to 43 mg/m ² , ^c	Optimize anti-emetic therapy AND reduce dose by 25%; if the patient is already receiving a reduced dose, reduce dose an additional 25% ^e
Grade 2 hand foot syndrome	100% of previous dose	1 st occurrence: Reduce dose by 25% 2 nd occurrence: Reduce dose another 25% (50% of original dose) ^d
Grade 3 or 4 hand foot syndrome	1 st occurrence: Reduce dose to 50 mg/m ² , if starting dose is 70 mg/m ² . 2 nd occurrence: Reduce dose to 43 mg/m ²	Discontinue therapy
Any grade neurocerebellar or ≥ Grade 2 cardiac toxicity	No dose modifications required ^d	Discontinue therapy
Sensory neuropathy	No dose modifications required ^d	No dose modifications required ^d

* Located at [REDACTED]

^a Fatigue and Grade 3 anorexia do not require dose modification.

^b Grade 1 diarrhea: 2-3 stools/day > pretreatment.

^c Grade 2 diarrhea: 4-6 stools/day > pretreatment; Grade 3 diarrhea: 7-9 stools/day > pretreatment; Grade 4 diarrhea: > 10 stools/day > pretreatment.

^d Any toxicity ≥ Grade 2, except anemia and alopecia, can justify a dose reduction if medically indicated.

^e Patients who require more than 2 dose reductions must be withdrawn from the study.

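### For repeated rucaparib-related ALT/AST elevation, the two-reduction cap in section 8.1 and the further steps permitted by footnote b of 8.22 contradict each other

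*Combined protocol and SAP*

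**What the plan says.** Section 8.1 is headed "8.1 Dose Modifications for Rucaparib (Based on Adverse Events in Tables 8.2 and 8.3" and has two modification columns. The row for the highest starting dose reads "600 mg BID 500 mg BID 400 mg BID"; the row for the next starting dose reads "400 mg BID 300 mg BID 200 mg BID". The note beneath the table is "No more than two dose reductions are allowed". It carries no exception for any toxicity.

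Section 8.22 deals with rucaparib when ALT or AST rises because of it. Its footnote b, attached to the dose-interruption column, says that if toxicity continues, "additional dose reduction steps are permitted; however, the investigator should contact ACCRU (see Protocol Resource page) before reducing to 300 mg BID". The next sentence begins "If a patient continues to experience toxicity despite dose reduction steps to 300 mg BID" and leads to discontinuation, unless ACCRU and the investigator agree otherwise.

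Footnote e of 8.3 says "Patients who require more than 2 dose reductions must be withdrawn from the study". The 8.3 table has dose columns for nal-IRI and 5-FU only.

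Section 7.12 names DL2-A as the recommended dose, with rucaparib at 600 mg twice daily for Phase Ib. Section 7.13 carries the Phase I recommended dose into Phase II without printing the figure. In Phase I, 400 mg twice daily is the rucaparib dose at the starting level DL1 and at DL 2-B.

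**The concern.** The cap in 8.1 is worded as absolute, and the permission in footnote b goes past it. Take a patient who started at 600 mg BID, is now on 400 mg BID, and again has a rucaparib-related ALT/AST elevation that calls for a reduction. One site could say that no reduction remains. Another could contact ACCRU and continue at 300 mg BID. Each could cite the protocol.

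At stake are consistent handling of a hepatic safety signal, rucaparib exposure in the expansion and efficacy parts, and what is recorded as a protocol deviation. ALT/AST increase is among the common rucaparib toxicities (above 10%) in section 15.17, so the ALT/AST table is likely to be used. How often a patient would need a third step is not stated.

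**Working it through.** No power, alpha or sample-size figure is involved. The check is a step count on the only rucaparib ladder in the protocol, followed by a check of scope.

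**Step count.** Inputs are the two 8.1 rows, the 8.1 cap of two, and the 300 mg BID level in footnote b.

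| Start (BID) | 8.1, reduction 1 | 8.1, reduction 2 | Lowest level in 8.1 | Level after which footnote b points to discontinuation |
|---|---|---|---|---|
| 600 mg | 500 mg | 400 mg | 400 mg | 300 mg |
| 400 mg | 300 mg | 200 mg | 200 mg | 300 mg |

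- From 600 mg: 500 is reduction 1, 400 is reduction 2 and 300 is reduction 3. Excess over the cap: 3 − 2 = 1. Skipping a level does not help, because the row fixes 400 mg BID as the second step and does not contain 300 mg BID.
- From 400 mg: 300 is reduction 1 and 200 is reduction 2. Footnote b points to stopping after one reduction where 8.1 lists two: 2 − 1 = 1 step fewer, unless otherwise agreed with ACCRU.

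The two texts therefore disagree in both directions. Footnote b is more permissive than 8.1 from 600 mg BID and more restrictive from 400 mg BID.

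**Does the 8.1 ladder apply to ALT/AST elevations?** The 8.1 heading ties it to Tables 8.2 and 8.3. Section 8.22 is numbered under 8.2 and has no ladder of its own, although its grade 4 row requires restarting at a reduced dose. The dose columns in 8.2 and 8.3 are for nal-IRI and 5-FU only. If the reference to 8.2 left out its subsections, the rucaparib ladder would be tied to two tables with no rucaparib column. Reading 8.1 as covering 8.22 is the more natural course.

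**Does either passage give way?** Neither cites the other, and neither states precedence.

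**Who is reached?** Footnote b belongs to 8.22, so the patients concerned are those with rucaparib-related ALT/AST elevation. For other non-hematologic toxicities, 8.21 calls for a one-level reduction at grade 3 or above. Footnote b is not attached there, and the 8.1 cap stands unopposed.

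**The case against.** The strongest reply is that 8.22 is a specific rule for one toxicity and so overrides the general ladder. Section 8.3 does cite 8.22 as a separate table and sends grade 3 ALT/AST there. That reading is plausible, but the text does not state it: the 8.1 note has no ALT/AST exception, and 8.22 does not say that it departs from 8.1.

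Two further points soften the conflict without removing it. Footnote b makes a site contact ACCRU before the disputed step, so a site following it would not act alone. However, it asks for contact rather than approval, and a site following 8.1 would never reach that call. Section 8.0 also makes the modifications binding for the first two cycles and advisory afterwards, and a third reduction would often fall later. Advice that both caps at two and permits more still does not tell a site what to do.

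A reader might infer three stronger things that the documents do not support:

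- That every patient with repeated toxicity is affected, meaning all 40 in Phase Ib and up to 52 in Phase II. Those figures are the planned enrolment, not the patients exposed to the conflict. Footnote b concerns ALT/AST only, and 7.51 allows other dose levels in Phase II.
- That footnote e of 8.3 is a third conflicting rucaparib rule. Its wording is not limited by drug, but it sits in a table for nal-IRI and 5-FU. It is unclear, not plainly contradictory.
- That the analysis denominators would shift. Under 16.32 and 16.42, a consented, eligible patient in the relevant population is evaluable after any protocol treatment, so later withdrawal does not change the denominator. Any effect on later tumour assessments is unquantified.

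**Conclusion.** The contradiction stands in a narrow form. For rucaparib-related ALT/AST elevation, the 8.1 note and footnote b of 8.22 give incompatible limits: one reduction more than the cap from 600 mg BID, and one fewer than the ladder lists from 400 mg BID. The 600 mg row matters most because 600 mg BID is the Phase Ib dose and the recommended dose carried to Phase II.

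This rests on reading 8.22 as falling under 8.1, as its numbering and its lack of a ladder suggest. If 8.22 was meant as an exception, the fault is that the protocol does not say so. The size is limited to patients with repeated rucaparib-related ALT/AST elevation who reach these steps, a number that cannot be derived from the documents. It is an inconsistency in safety instructions, with no demonstrated effect on the primary analyses.

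**What to change.** The sponsor must reconcile the 8.1 table and note with footnote b of 8.22 so that one maximum number of rucaparib reductions and one lowest level applies for each starting dose. Alternatively, it must state expressly which passage governs ALT/AST elevations and add the cross-reference in both places. It should also make clear whether footnote e of 8.3 counts rucaparib reductions or only those of nal-IRI and 5-FU. Which rule is right is for the clinical team. The cost is amendment wording; sample size and analysis do not change.
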